### Consent Process

- Complete the consent section in the iRIS Submission Form.

### Subject's Capacity to Give Legally Effective Consent

- If subjects who do not have the capacity to give legally effective consent are included, describe how diminished capacity will be assessed. Will a periodic reassessment occur? If so, when? Will the subject be consented if the decisional capacity improves?

If patient is cognitively impaired, they will be excluded from the study per study protocol.

### Study Interventions

- If not already presented in #4 above, describe study-related treatment or use of an investigational drug or biologic (with dosages), or device, or use of another form of intervention (i.e., either physical procedures or manipulation of the subject or the subject's environment) for research purposes.

Study interventions presented in #4 above.

## Risk/Benefit Assessment

- Include a thorough description of how risks and discomforts will be minimized (per 45 CFR 46.111(a) (1 and 2)). Consider physical, psychological, legal, economic and social risks as applicable. If vulnerable populations are to be included (such as children, pregnant individuals, imprisoned persons or cognitively impaired adults), what special precautions will be used to minimize risks to these subjects? Also identify what available alternatives the person has if he/she chooses not to participate in the study. Describe the possible benefits to the subject. What is the importance of the knowledge expected to result from the research?

## Potential Risks

In the proposed study, the potential risks to participants are minimal and rare. The potential risks are associated with (1) confidentiality related to the use of smartphones and a mobile app, and self-report data, and (2) potential emotional upset due to questioning about thoughts, feelings, and personal/family history of cancer when completing intervention sessions and assessments. First, breach of confidentiality is a possible risk. This will be clearly stated in the consent form. All efforts will be made to maintain confidentiality. Participants' data and research records will be carefully stored (See protections against risk). Second, participants will be asked about their thoughts and feelings about their cancer, pain, and symptoms; thus, it is possible they may experience distress. The psychological risk associated with answering questions is expected to be minimal. Although some participants may find certain questions or topics to be upsetting, heightened awareness of existing psychosocial and practical needs may be the first step in resolving these concerns. The recruitment letter will clearly acknowledge the voluntary nature of participation and patients will have the ability to decline further contact from study personnel at any time (i.e., to opt out). Participants will be fully informed about the study during the informed consent process and instructed to decline to answer any question or to discuss any issues they find troubling. If a participant reports significant distress during study participation, the study team will consult with Drs. [name] and [name] (licensed clinical psychologists). If the participant requires additional treatment, we will initiate the appropriate referral. Our team has extensive experience conducting psychosocial intervention trials with patients with cancer and have not encountered significant psychological distress caused by study participation. Moreover, patients with cancer often report benefits from participating in psychosocial research. Thus, the risk of psychological distress is minimal and these safeguards should be adequate.

## Adequacy of Protection Against Risks

**a. Informed consent and assent.** Recruitment will take place through the Duke Cancer Institute (DCI), an NCI-designated Comprehensive Cancer Center. Recruitment procedures will receive Institutional Review Board (IRB) approval and comply with HIPAA regulations. This study will follow the same recruitment procedures used in previous RCTs conducted by our team with cancer patients, including colorectal cancer patients, and including multiple federally-funded projects conducted by the Duke Pain Prevention and Treatment Research Program. In March of 2019, Duke implemented a revised Recruitment and Engagement Policy that allows Duke researchers to utilize "direct-to-patient" or "cold contacting" methods. Rather than requiring physician approval before approaching potential participants, Duke researchers can use IRB-approved methods of direct contact. The Duke Notice of Privacy Practices informs all patients that Duke is an "opt-out" institution. That is, patients' medical records may be reviewed for research purposes, and patients may be contacted about research unless they "opt-out" of such contacts. This policy change was largely driven by respect for patients' autonomy (i.e., empowering patients to choose whether to participate in research), need for increased patient awareness of research opportunities, and research demonstrating "op-out" methods result in stronger recruitment rates and more representative study samples.

Under a HIPAA waiver, potentially eligible patients will be identified by study staff using the Duke Enterprise Data Unified Content Explorer (DEDUCE) to query the Duke Electronic Medical Record (EMR) on a weekly basis. After a careful chart review to verify initial eligibility (e.g., age  $\geq$  18 years, English speaking, stage I-IV colorectal cancer diagnosis, pain score of 4 or greater at a Duke clinical oncology appointment), study staff will mail potential participants a study brochure and introductory letter signed by the Principal Investigator. The letter explains that the patient may be eligible to participate in a research study evaluating a mobile app behavioral cancer pain intervention for patients with cancer and pain. The letter includes a number to call if the patient is interested in learning more about the study (or would like to opt out) and explains that a study staff member will contact them in around five days to discuss the study. Patients will then be called by highly trained study staff to assess interest. All patients who meet eligibility criteria will be contacted *unless they opt out*. Consistent with Duke's direct-to-patient

recruitment guidelines, we will only attempt to contact patients a maximum of three times if we are unable to reach them. If a patient is interested when contact is made with a study team member, they will be provided with information about the study, its purposes, requirements, and time commitment. Interested patients will complete a scripted telephone screening (e.g., symptom ratings) compliant with DUHS IRB policies to confirm full eligibility. Those who do not pass the telephone screening but ask for resources will be provided with a list of free resources available through the Duke Cancer Patient Support Program (e.g., financial support, individual and couple counseling). Eligible patients who wish to enroll in the study will complete electronic consent using REDCap. Those who do not have access to the internet for completing the electronic consent form will be mailed a paper copy. A member of the study team will provide private consent and answer any questions that the potential participant may have. This remote, direct-to-patient recruitment approach has allowed us to efficiently reach more patients while reducing numerous obstacles encountered with methods that require physician time and clinic resources. We have successfully recruited for many trials using this well-developed recruitment system.

**b. Protections against risk.** Risks associated with the proposed study are low and not expected, but nonetheless will be carefully monitored. The study investigators, including Drs. [name] (PI) and [name] (Co-I), both licensed clinical psychologists, and [name] (Co-I), medical oncologist, and the study team will take all precautions possible to avoid and minimize potential risks. The consent form will address all possible risks. Should any of these occur, appropriate emergency care will be provided. The proposed significance of study findings outweighs this risk. Here we detail all procedures for protecting against or minimizing potential risks.

*Confidentiality.* Breach of confidentiality will be a potential risk noted in the consent documents and verbally discussed with the patients during recruitment. Protection of confidentiality is a central priority. All efforts will be made for confidentiality to be maintained by using study ID numbers to identify participants' research records and by having a limited number of individuals who have access to identifying information. As noted, participants' data and research records will be protected using subject identification numbers. A document linking participant names to subject identification numbers will be stored separately from data and research records in a password-protected database. All paper research records (e.g., paper consent documents) will be kept in a locked file cabinet in a locked office. Electronic data files (e.g., audio recordings of sessions) will be stored on an Office of Information Technology (OIT) secured DUMC network drive. This drive will be backed up and secured by the OIT department on a daily basis. Only approved study staff will have access to the research records. There is some risk of loss of confidentiality inherent to the use of videoconferencing to conduct the PCST-Video intervention sessions. To protect patient privacy, we will use Zoom videoconferencing, which has standard internationally-recognized and accepted encryption algorithms. Zoom meetings will have end-to-end encryption (E2EE). In a meeting with E2EE enabled, no one except each participant—not even Zoom's servers—has access to the encryption keys being used to encrypt the meeting. No recording will be conducted within Zoom. Audio-recording of intervention sessions will be conducted using Voice Recorder on the study teams' encrypted Duke-issued and maintained laptops. Audio-recordings will be saved to the DUMC server and deleted from the laptop. All audio-recordings will be deleted at the end of the study. All study staff will be required to complete Duke University Health System Institutional Review Board's online training course (i.e., Protecting Research Subjects) as well as human research subjects' protection training and certification through the Collaborative Institutional Training Initiative (CITI) program, both of which address confidentiality. The anticipated significance of the study results and likely benefits to participants outweigh the minimal risks.

Two password protected databases will be used for this study to ensure confidentiality. First, a tracking database will be used for recruitment and follow-up. This data will house information related to tracking the participants in the study, such as phone numbers and addresses. Identifying information will be kept separate from research records. No medically sensitive or outcome data will be stored in this database. This database will also track nonparticipants (i.e., those who have declined participation) only to the barest minimum to ensure that they are not contacted again about participation. At the end of the study, all identifiable data of non-participants such as their names will be deleted. Tracking data on participants will be retained for the usual required period. Second, all study data will be stored in a separate password protected REDCap database without any personal identifiers. Data in this database will be derived from patients' direct input into the electronic patient reported outcomes system which is an online survey system; data entered into this system is stored on a secure server housed behind the DUMC firewall. Only a unique study identification number will link the electronic data to the study data file. Patient data that goes into the mobile behavioral pain application (PainPac) will only be identified with a number and the app is designed so that data, like self-report data, is stored on a secure server housed behind the DUMC firewall. The tracking data and study data will be stored in a file on a secure DUMC psychiatry server which can only be accessed by necessary members of the research team. Access to the Duke network requires a password protected, 128-bit encrypted virtual private network connection provided by Cisco systems.

The PI has completed Duke University Health System Institutional Review Board's online training course: Protecting Research Subjects, as well as human research subjects' protection training and certification through the Collaborative Institutional Training Initiative (CITI) program, both of which address confidentiality. All other individuals involved in this study will be required to complete these courses and ongoing training. The risks associated with the proposed study are low. The PI and investigative team have conducted research in the proposed area and have not encountered medical emergencies or significant

psychological distress caused by study procedures. In fact, participation in the proposed study procedures and intervention is associated with few negative side effects and potentially multiple benefits to physical health, mood, and quality of life. The proposed significance of study findings outweighs the limited risk.

**Smartphone Security Measures.** Smartphones used for this study will be configured for minimal use necessary for the purpose of the study and will not be used for personal use by staff or study participants. Specifically, the following steps will be taken: 1) Study staff will keep the operating system on the most current version. 2) We will enable encryption on the device and verify that data protection is enabled, set "require passcode" to immediately, and enable erase data to "automatically erase the device" after 10 failed passcode attempts. 3) We will set Auto-Lock. 4) Study staff will use Restrictions to restrict any unnecessary access including changing account settings. 5) We will reset smartphones between use for different participants. 6) At end of device life, we will send the device to Duke Procurement Surplus & Salvage for secure destruction. Study participants will have the option to use a Duke Health study smartphone or their personal smartphone. The study mobile application will be made available to participants regardless of whether they use a study smartphone or their personal smartphone.

**Mobile App Data Storage and Security.** Pattern Health (Durham, NC) is a digital health company specializing in patient-centered web and mobile products for clinical and medical research and health data tracking and analysis, with expertise working with wireless devices and improving patient engagement. Pattern Health has an established relationship with the PI and study team, as well as other researchers at Duke, the Duke Medicine Information Security Office (ISO), Duke Health Technology Services (DHTS), and the Duke Digital Strategy Office. Pattern Health is contracted for the implementation of a mobile app for use in the current study, which is similar to the mobile app developed and tested *adjunctively* in [name] prior work. App data is stored in a MySQL database. This is a standard security feature, which allows the database to be kept separate from the web server to protect access to the database. In addition, the hard drive of the database machine will be encrypted, which will provide security in case the hard drive is physically compromised. Duke ISO, DHTS, and the Duke Digital Strategy Office will review and approve Pattern Health's documents outlining their data collection process, and data storage and security for the proposed study; these Duke entities previously approved Pattern Health's data collection, storage and security for [name] ACS RSG and previous NIH R21 projects, and these procedures will be the same for the proposed R21 project.

**Emotional Upset.** The risk of emotional upset associated with intervention sessions and assessments is rare, and all interactions with study participants will be under the direction of PI [name], a licensed clinical psychologist. To address risks related to the possibility of psychological distress, participants will have the option of withdrawing from the study without loss of benefit. Interventionists and study staff in this trial will have experience working with distressed patients with chronic disease. They will be trained, specifically in the context of this trial, to monitor participants' psychological status and for any signs that participants are experiencing high levels of physical or emotional distress that need to be addressed outside the context of this trial. Interventionists will be trained to report any concerns immediately and directly to the PI. If this is determined to be the case, the PI will work directly with the participant to move forward in a way that is in the best interest of the patient. No participant will be kept in the trial if they are experiencing increased or extreme distress. As noted previously, intervention sessions will be audio-recorded and reviewed by Drs. [name] and [name] to ensure the delivery of effective and ethical treatment. Further, the study Clinical Research Coordinators (CRC) will monitor daily all assessments with particular attention paid to the suicidal ideation item on the Brief Symptom Inventory. The CRC will immediately report all elevated responses on this item to the study PI. [name] (PI) will also be contacted when *any* emotional distress is identified in a participant. The study assessments have been well validated for use with patients with cancer. *Moreover, these assessments were specifically chosen for their brevity in order to reduce patient burden.* Participants will be reminded that they can omit responses to any questions that they do not feel comfortable answering. Again, all research personnel who have direct contact with patients will be trained to observe and immediately report any adverse events to [name]. [name] will report any adverse events to the institutional review board at Duke University and to NIH, and will consult Drs. [name] (licensed clinical psychologist and senior level faculty Co-I), and [name] (experienced physician) to collaboratively develop a course of action, which may involve facilitating referrals for additional treatment. These referrals may be made to various members of the Duke Cancer Patient Support Program, including psychiatrists, psychologists, and medical family therapists, as appropriate. Participants will be provided with emergency contact numbers as well as access to numerous support services offered through the DCI. [name] works directly with Cancer Patient Support and Care at Duke Cancer Institute as a practicing licensed clinical psychologist and as a supervisor to psychology trainees (i.e., advanced graduate students, clinical psychology pre-doctoral interns) and [name] (Co-I) directs the clinical psychology training program within the Duke Cancer Patient Support Program at the Duke Cancer Center. Both Drs. [name] and [name] are integrated into the psychosocial clinical care program at the Cancer Center and have experience referring cancer patients who are distressed to appropriate psychosocial or psychiatric care within this large team of mental health professionals. [name] will use these same resources when making referrals for distressed participants in this study. The PI and entire investigative team have conducted research in the proposed area and have not encountered significant psychological distress caused by study procedures. In fact, participation in the proposed study procedures and intervention is associated with few negative side effects and potentially multiple benefits to physical health, mood, and quality of life. The proposed significance of study findings outweighs the limited

risk. Finally, it is important to note that all participants will continue to receive usual care from their medical team. Consistent with numerous behavioral pain intervention protocols in our group, no participant will be asked to change or decline any strategies for pain management based on their participation in the study.

### Potential Benefits of the Proposed Research to Research Participants and Others

There are numerous potential benefits of the proposed research. Colorectal cancer patients with persistent pain may learn ways to enhance their pain coping and may experience significant decreases in pain and disability; the proposed intervention may lead to improvement in participants' pain and pain-related outcomes. There are currently no evidence-based standalone mobile app behavioral cancer pain interventions for patients with cancer and pain. This study has the potential to be of great benefit to this heavily burdened patient population. We also anticipate the results from this study will spur more research into mobile health-based behavioral symptom self-management interventions for patients with cancer and pain.

### Costs to the Subject

- Describe and justify any costs that the subject will incur as a result of participation; ordinarily, subjects should not be expected to pay for research without receiving direct benefit.

No cost to the subject.

### Data Analysis & Statistical Considerations

- Describe endpoints and power calculations. Provide a detailed description of how study data will be analyzed, including statistical methods used, and how ineligible subjects will be handled and which subjects will be included for analysis. Include planned sample size justification. Provide estimated time to target accrual and accrual rate. Describe interim analysis including plans to stop accrual during monitoring. Phase I studies, include dose escalation schema and criteria for dose escalation with definition of MTD and DLT.

**Statistical Design and Analyses.** A pilot trial (N=60) will be used to compare PainPac (n=30) to PCST-Video (n=30) on measures of feasibility (primary aim), burden, acceptability, engagement, and initial pain-related outcomes. Sample size was informed by pilot trial guidelines for RCTs of behavioral interventions,  and past similar studies, that suggest 30 participants per condition is sufficient for determining feasibility and acceptability, and feasibility of a future definitive trial. We anticipate no more than 25% attrition by 1 month post- baseline, based on previous psychosocial studies with cancer patients. Both groups of 30 participants are needed because we aim to demonstrate two types of feasibility: feasibility of the PainPac app, which only requires the 30 PainPac participants, and feasibility of the subsequent larger RCT (i.e., recruitment, assessments), which requires all 60 PainPac and PCST-Video participants. We are recruiting both sexes and all genders, and we expect a nearly equal sample size between sexes. To account for sex as biological variable, we will describe all outcomes disaggregated by sex. We will examine intervention effects and use this data to optimize PainPac. Aim 1. Feasibility (accrual, attrition, adherence), burden, acceptability, and engagement will be assessed post-treatment and descriptive statistics will be produced for PainPac and PCST-Video. Overall trial feasibility benchmarks include reaching target accrual (N=60) within 15 months and <25% attrition by 1 month post- baseline. Descriptive statistics will be used to report non-eligibility and refusal. Data of non-completers will be compared to completers. 75% completed will serve as our feasibility benchmark. If >25% of consented patients drop out, PainPac will not be considered feasible. We do not expect attrition to be greater in the PainPac condition compared to PCST-Video. PainPac feasibility benchmarks include protocol adherence indicated by calculating the degree to which participants are willing/able to complete study assessments (pre, post, follow- up) and the 4 PainPac skills modules or 4 PCST-Video sessions. 75% completed will serve as our benchmark. If >25% of consented patients do not complete the intervention (modules /sessions and assessments), PainPac will not be considered feasible. We expect adherence in the PainPac condition will be at least comparable to PCST-Video. Patient Burden will be measured as a continuous variable by assessing physical, emotional, and financial burden of engaging in the study intervention. We expect burden will not be greater in PainPac compared to PCST-Video. Patient Engagement will be assessed by electronic app data (e.g., PainPac weekly log-ins) and patient self-report defined as the

number of times per week they practice the coping skills.  $\geq 3$  times/week will serve as the benchmark; if participants log into PainPac and/or practice the coping skills  $< 3$  times/week, PainPac will not be considered engaging. We expect engagement in PainPac will be at least comparable to PCST-Video. Acceptability will be indicated by 80% of patients reporting satisfaction with PainPac and PCST-Video ( $M=3.2/4$ ) on the CSQ. Aim 2. Between-group differences at follow-up will be characterized using Cohen's  $d$  and 95% confidence intervals. Consistent with recommendations for small pilot RCTs of behavioral interventions, we propose a conservative approach that focuses on describing effect size estimates and their variability instead of testing for significant group differences. As this is a small trial intended to provide signals the intervention is promising and data for a larger trial, all pre- to post-intervention and 1 month variables will be characterized using graphs/plots and descriptive statistics (e.g., mean, standard deviations, range). We will examine the pattern of findings to determine the best analytic plan for the subsequent trial. Pain may vary based on pain medications and disease stage/treatment; we will describe these variables and include them, when appropriate, as covariates in future larger trials. The subsequent trial will be fully powered to test two active conditions. Given our proposed sample size ( $N=60$ ), an a priori power calculation using G-Power suggests we will have  $>80\%$  power to detect medium-sized effects of  $d=0.74$  ( $\alpha=0.05$ , two-tailed). However, as noted above, our analytic plan focuses on describing between-group differences rather than testing for significant effects. Aim 3. We will use methods from applied thematic analysis to analyze interview data. First, we will create a codebook a priori that corresponds to major content areas from the interview guide. The codebook will include a coding matrix with categories, codes, and definitions. The analysts ([name] and a study member) will segment interview transcripts into major content areas using Nvivo and then use an inductive and iterative approach to identify data-driven codes. As new codes emerge, they will be applied to previously coded sections until all relevant information is captured. All codes will be grouped into themes and subthemes. The analysts will meet to discuss coding and resolve discrepancies in interpretation, and maintain an audit trail of coding and analytic decisions. The study team will review the qualitative findings and develop action steps for modifying the protocol. All data will be used to optimize PainPac for a large randomized clinical effectiveness trial. We will optimize areas related to patient preferences, barriers, beliefs, and cultural tailoring to increase usability and engagement and meet user needs.

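### Both rules that can declare PainPac not feasible count all consented patients, not the 30-patient PainPac arm on which the plan bases app feasibility, so losses in PCST-Video can decide the verdict

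*Combined protocol and SAP*

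**What the plan says.** All the relevant text is in the Statistical Design and Analyses paragraph under Data Analysis & Statistical Considerations. It distinguishes two kinds of feasibility: "feasibility of the PainPac app, which only requires the 30 PainPac participants", and feasibility of the later, larger RCT, "which requires all 60 PainPac and PCST-Video participants".

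Two failure rules follow.

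- **Attrition.** The benchmark is introduced at trial level: "Overall trial feasibility benchmarks include reaching target accrual (N=60) within 15 months and <25% attrition by 1 month post- baseline". Its failure clause gives a verdict on the app: "If >25% of consented patients drop out, PainPac will not be considered feasible".
- **Adherence.** The benchmark is introduced at app level: "PainPac feasibility benchmarks include protocol adherence". It is measured by whether participants "complete study assessments (pre, post, follow- up) and the 4 PainPac skills modules or 4 PCST-Video sessions", and the failure clause is "If >25% of consented patients do not complete the intervention (modules /sessions and assessments), PainPac will not be considered feasible".

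The plan also promises descriptive statistics for each condition and states an expectation: "We do not expect attrition to be greater in the PainPac condition compared to PCST-Video". The Randomization paragraph of Design & Procedures places randomisation after consent and baseline assessment.

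**The concern.** Neither failure clause states a denominator that fits the plan's own 30/60 split, and the two miss it in opposite ways. The attrition rule sits under a trial-level benchmark, where 60 is the natural denominator, but its verdict is on PainPac. The adherence rule sits under an app-level benchmark, where 30 is natural, but it counts therapist sessions, which only PCST-Video patients receive. Because consent precedes randomisation, the literal denominator takes in both arms and also anyone lost before allocation.

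Feasibility is the primary outcome. The Purpose of the Study section makes it, together with promise of benefit, the condition for the larger RCT. If the arms lose patients at different rates, the literal rule can fail an app with good retention or let through one with poor retention. By-arm summaries would show the divergence, but no by-arm pass/fail rule is attached to them, so the denominator would have to be settled after the results are known.

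**Working it through.** The plan gives no calculation for the 25% and 75% benchmarks, so there is no stated figure to reproduce on this point. The check compares the two denominators directly.

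**Inputs.** 30 patients per arm and failure above 25% come from the plan. A PCST-Video loss of 16% is borrowed from the earlier videoconference trial described in Background & Significance; it is not an assumption of this plan. All other loss rates are assumptions chosen to show a range. Arms are treated as independent binomials. No losses between consent and randomisation are modelled.

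**Thresholds.** The smallest count exceeding 25% of n is floor(0.25n) + 1.

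- PainPac arm, n = 30: fails at 8 or more (8/30 = 26.7%), not at 7 (23.3%).
- Pooled, n = 60: fails at 16 or more (16/60 = 26.7%), not at 15 (25.0%).

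**Cases where the verdicts part.**

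- PainPac 5/30 and PCST-Video 11/30 lost: 5 + 11 = 16, and 16/60 = 26.7%. The pooled rule fails PainPac, although its own loss is 16.7%.
- PainPac 11/30 and PCST-Video 3/30 lost: 11 + 3 = 14, and 14/60 = 23.3%. The pooled rule does not fail PainPac, although its own loss is 36.7%.

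**Probability that the attrition rule is passed.** Let X and Y be the losses on PainPac and PCST-Video. The pooled rule is passed with probability P(X + Y ≤ 15), the arm rule with P(X ≤ 7). The verdicts differ when exactly one of the two is passed.

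| True loss, PainPac / PCST-Video | Pooled (60) | PainPac arm (30) | Verdicts differ |
|---|---|---|---|
| 30% / 16% | 0.71 | 0.28 | 0.44 |
| 35% / 16% | 0.53 | 0.12 | 0.42 |
| 40% / 16% | 0.36 | 0.04 | 0.31 |
| 16% / 35% | 0.53 | 0.91 | 0.39 |
| 16% / 16% | 0.98 | 0.91 | 0.09 |
| 20% / 20% | 0.87 | 0.76 | 0.18 |
| 25% / 25% | 0.57 | 0.51 | 0.25 |

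These figures are for the attrition rule alone. PainPac must also pass the adherence rule, so an overall pass cannot be more likely than shown.

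**Sensitivity to exactly 25%.** The table counts 15/60 as not failed, as the failure clause implies. The trial-level benchmark asks for less than 25%, which 15/60 does not meet. With a pass at 14 or fewer, the pooled column becomes 0.60, 0.41, 0.25, 0.41, 0.95, 0.79 and 0.45. The gap narrows when PainPac loses more (0.41 against 0.12 at 35%/16%) and widens in the reverse case (0.41 against 0.91). At 25%/25% the pooled figure drops below that of the arm (0.45 against 0.51). With equal losses the rates of disagreement do not change.

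**The case against.** The strongest reply is that this is loose wording. The plan says that app feasibility needs only the 30 PainPac participants, so a sensible reader applies a PainPac verdict to those 30. The mention of sessions may only reflect that adherence is computed in both arms. The Aim 1 hypothesis attaches the attrition and adherence limits to PainPac and expects results at least comparable to PCST-Video, so the plan does intend to look at differences between arms. That reading is possible, and the intention may well have been the PainPac arm. But the same hypothesis lists accrual of 60 under PainPac, so it does not define a 30-patient rule, and the comparability statements are expectations rather than decision rules.

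A second reply is that the large gaps rest on unequal losses that the plan does not expect. This is correct as far as it goes: with equal losses the pass probabilities differ by only 0.06 to 0.11 (0.57 − 0.51 at 25%; 0.87 − 0.76 at 20%). Individual verdicts still disagree in 9% to 25% of trials, and a comparison of a standalone app with therapist-led delivery ought to be able to reveal unequal loss.

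A third is that consented patients are a defensible denominator for trial feasibility, since that concept covers recruitment and assessments. This has some force at trial level. It does not justify using that denominator for a verdict on the app.

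Finally, this is a descriptive pilot in which no test depends on the rule. That limits the consequence, but the pass/fail rule is what the primary outcome delivers.

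**Conclusion.** The concern holds, and the point should be fixed. The plan sets a 30-patient basis for app feasibility and then writes both PainPac failure rules on an unrestricted group of consented patients. Followed as written, the rules can give the wrong verdict on the app in either direction. The effect is large when the arms differ: about 0.4 in the probability of passing attrition at 35% against 16% loss, either way round. It is modest when they do not. The contradiction in the text depends on no assumption. The probabilities depend on 30 per arm, independent arms and illustrative loss rates, and the pooled figures also depend on how exactly 25% is treated.

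**What to change.** Before data are seen, state the denominator of each rule:

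- **PainPac verdicts.** Use participants randomised to PainPac. PainPac is not feasible if more than 25% drop out by the plan's attrition time point, or if more than 25% do not complete the 4 modules and the assessments. That means 8 or more for any arm size from 28 to 31, including the planned 30.
- **PCST-Video.** Report it separately by the same definition, with the 4 sessions in place of the modules.
- **Trial-level attrition.** Keep this benchmark on all randomised participants, word its verdict as one about the trial, and say how exactly 25% (15/60) is handled.
- **Losses between consent and randomisation.** Report these as a separate count. If the investigators prefer consented patients as the trial-level denominator, they should say so there and confine it to the trial verdict.

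This costs a few sentences and needs no new data. The price is precision. On about 30 patients the exact 95% interval is wider (23/30: 58% to 90%; 45/60: 62% to 85%), and an app with a true 25% loss passes the attrition rule about half the time (0.51, against 0.57 pooled when both arms lose 25%). The plan's own 30-patient basis already implies that imprecision.
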